7.3. Interruption and Termination of Dosing

As described in Section 7.1 , administration of study glucagon is only permitted if a subject meets the criteria for a hypoglycemic steady state. Administration of study glucagon to a subject not in a hypoglycemic steady state will be deemed a major protocol violation.

At 30 minutes post-glucagon administration, if a subject fails to achieve an increase of plasma glucose of at least 20 mg/dL (1.11 mmol/L), appropriate measures (oral or IV glucose) will be taken at the Investigator's discretion.

Post-administration of study glucagon, if a subject exhibits signs of coma or convulsions, a IV bolus dose of dextrose will be given per standard of practice. Signs and symptoms should be monitored, and if the subject's condition fails to improve in a timely manner, additional dextrose or other medical interventions may be given at the Investigator's discretion.

Note: A second dose of study glucagon should NOT be administered as hypoglycemia rescue in this context.

Euglycemia will be confirmed and the subject should be medically stabilized per Investigator discretion before being released. If applicable, completion of a subsequent treatment visit will be at the discretion of the Investigator in consultation with the Medical Monitor.

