9.2. Blinding

For this study, the subject but not the Investigator will be blinded (single-blind design). The G-Pen 1 mg device makes a series of two audible clicks when the dose is administered. To help ensure blinding, the subject will wear headphones that play music to mask sound during dosing procedures. The subject's ability to see the injection equipment and procedure will be obstructed by use of a blindfold placed prior to dosing. The subject will be instructed not to talk with the study staff about their impression of which product he/she received at a visit until the end of the second treatment sequence. At which time, the subject will be asked to guess what their first treatment was, and what their second treatment was from the choices of "Xeris Glucagon, G-Pen, administered by auto-injector" or "Comparator Glucagon, GlucaGen Hypokit, administered by needle and syringe". The subject's responses will be recorded in the electronic Case Report Form (eCRF) for the Subject Study Drug Assignment Questionnaire (see [Appendix 5](#)).

In the event that a subject is inadvertently unblinded during one or both of the treatment sequences, the investigator will note the event as a protocol violation, and the subject will be allowed to continue further study treatments as per the protocol.

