12.7. Withdrawal Due to Adverse Events

Withdrawal due to AE should be distinguished from withdrawal due to insufficient response and recorded on the appropriate eCRF. When a subject withdraws due to an SAE, the SAE must be reported in accordance with the reporting requirements (see Section 12.9).

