4.4 Unblinding

This is a single-blind study. Only the subjects are blinded for treatment. The investigator and clinical staff will be aware of the treatment. Thus, there is no unblinding requirements needed for the study.

In the event that a subject is inadvertently unblinded during one or both of the treatment sequences, the investigator will note the event as a protocol violation, and the subject will be allowed to continue further study treatments as per the protocol.

At the end of the study, the subjects will be asked to guess what their first treatment was, and what their second treatment was from the choices of “Xeris Glucagon, G-Pen, administered by auto-injector” or “Comparator Glucagon, GlucaGen Hypokit, administered by needle and syringe”. The subject’s responses will be recorded in the electronic Case Report Form (eCRF) for the Subject Study Drug Assignment Questionnaire.

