5.1.3 Per-Protocol Population (PP)

The Per-Protocol (PP) population is defined as all randomized patients who during both study periods successfully receive a dose of both study drugs (G-Pen followed by GlucaGen Hypokit or GlucaGen Hypokit followed by G-Pen) and have no any major protocol deviations. The actual treatment received will be used for analysis.

Primary endpoint comparison and secondary efficacy analyses will be performed for ITT, mITT and PP populations.

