6.5 Analysis of Primary Endpoint

The primary endpoint analysis will be based on the risk difference in rates of failing to achieve Positive Plasma Glucose Response (PGR) of G-Pen versus GlucaGen Hypokit and a 95% CI will be calculated. Non-inferiority will be declared if the upper limit of the 95% confidence interval for the difference in failure rates is $\leq 5\%$; where the absolute failure rate of G-Pen treatment is $\leq 5\%$. This analysis will be repeated for ITT, mITT and PP populations.

Subjects who are missing the primary endpoint for a study treatment will be considered as having a failure in the primary analysis for that treatment administration. This imputation will be conducted for both the ITT and the mITT populations. If a subject received the same two treatment administrations for both periods (Period 1 and Period 2), only the visit with the planned treatment received will be included in the primary analysis and the subject will be considered a failure in the primary analysis for the for unreceived treatment administration (ITT, mITT). For all other analyses, data will be included for only the planned treatment received in those analyses.

A sensitivity analysis will be performed for where all missing data will be considered a success and the same analysis as above completed.

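### When a failed first dose is not followed by a second visit, PP drops the failure and ITT/mITT offset it, which pulls the non-inferiority difference toward zero

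*Protocol*

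**What the plan says.** Protocol 7.3 covers a subject whose glucose has not risen by at least 20 mg/dL 30 minutes after glucagon, or who shows coma or convulsions after dosing. For the time once the subject is stable, it adds: "If applicable, completion of a subsequent treatment visit will be at the discretion of the Investigator in consultation with the Medical Monitor". No criteria are given. On blinding, SAP 4.4 states: "The investigator and clinical staff will be aware of the treatment". Protocol 12.7 foresees non-response as a reason for leaving: "Withdrawal due to AE should be distinguished from withdrawal due to insufficient response".

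Three scoring rules then apply.

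- **PP** (SAP 5.1.3) is limited to "all randomized patients who during both study periods successfully receive a dose of both study drugs". Protocol 13.3 also requires both doses.
- **ITT and mITT** (SAP 6.5): "Subjects who are missing the primary endpoint for a study treatment will be considered as having a failure in the primary analysis" for that treatment.
- **Declaration** (SAP 6.5): the upper 95% limit for the difference in failure rates must be at most 5%, and the G-Pen failure rate itself at most 5%. The analysis is run in ITT, mITT and PP, and the SAP does not say which population decides. A sensitivity run scores all missing data as success, but it is not part of the rule.

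The only interval shown is in SAP Appendix 2: PROC FREQ with riskdiff on treatment by response, which is unpaired. SAP 6.1 allows the final code to differ.

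**The concern.** Missing = failure is usually accepted in a non-inferiority trial because ordinary missing test-drug doses count against the test drug. Here the gap can follow from the first result. Take a subject who receives G-Pen first, fails, and is not dosed again. PP removes the pair. ITT and mITT keep the G-Pen failure but add a GlucaGen failure that nobody observed, so the pair contributes 0 to the difference instead of +1.

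Both protocol and SAP expect response close to 100%, so a handful of failures decides the result. PP is the usual check on ITT in such a trial, yet on this point its estimate moves the same way. Agreement between the two is therefore weak reassurance.

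**Working it through.** **Inputs from the documents.** N = 122 randomized (SAP 4.2), taken as 61 per sequence. The 122 follows from 111 × 1.10 = 122.1. The 111 cannot be re-derived because no odds-ratio margin is stated, but nothing below uses it. The margin is 5%, the absolute G-Pen condition is 5%, and the limit is unpaired as in SAP Appendix 2.

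**Assumptions.** f is the fraction of first-period failures not dosed again; no document gives it, so it runs from 0 to 1. The true failure rates are chosen so that the difference sits at the margin. Periods are independent.

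**Does the 7.3 event match primary failure?** Largely. The SAP's primary failure also requires staying below 70 mg/dL. Dosing takes place at 42 to below 54 mg/dL. Since 70 − 20 = 50, only a subject starting above 50 mg/dL can reach 70 with a rise of less than 20.

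**One data set.** Upper limit = d + 1.96 × √[pG(1−pG)/nG + pR(1−pR)/nR], where G is G-Pen and R is GlucaGen. Take 3 G-Pen failures and no observed GlucaGen failure.

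| Scoring | G-Pen | GlucaGen | d | Upper limit | Rule met? |
|---|---|---|---|---|---|
| All visits done | 3/122 | 0/122 | 2.46% | 5.21% | no |
| One visit cancelled, ITT/mITT | 3/122 | 1/122 | 1.64% | 4.82% | yes |
| One visit cancelled, PP | 2/121 | 0/121 | 1.65% | 3.92% | yes |
| One visit cancelled, missing = success | 3/122 | 0/122 | 2.46% | 5.21% | no |

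ITT row: 0.0164 + 1.96 × √(0.0246 × 0.9754/122 + 0.0082 × 0.9918/122) = 0.0164 + 1.96 × 0.0162 = 0.0482.

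The effect on ITT has a ceiling. With 6 G-Pen failures, all in period 1 and all cancelled, the ITT difference is 0 but the limit is 5.43%, so ITT still fails; PP shows no failures at all. With 7, the G-Pen rate is 7/122 = 5.74% and the absolute condition fails in ITT.

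**Expected shift.** Half of each drug's doses fall in period 1. With the same f for both drugs and no other dropout, the mean ITT difference is (pG − pR) × (1 − f/2). At 5% v 0% that is 5.0 points at f = 0, 3.75 at f = 0.5 and 2.5 at f = 1.

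**False declaration by simulation** (full rule, unpaired limit, no other dropout):

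| True failure, G-Pen v GlucaGen | f | ITT | PP | Missing = success |
|---|---|---|---|---|
| 5% v 0% | 0 | 5% | 5% | 5% |
| | 0.5 | 10% | 16% | 5% |
| | 1 | 14% | 41% | 5% |
| 6% v 1% | 0 | 5% | 5% | 5% |
| | 0.5 | 6% | 15% | 5% |
| | 1 | 7% | 35% | 5% |
| 7% v 2% | 0 | 4% | 4% | 4% |
| | 0.5 | 4% | 11% | 4% |
| | 1 | 4% | 29% | 4% |

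The f = 0 rows exceed the nominal 2.5% because a Wald limit is unreliable with so few events. That is a separate matter; the comparison here is with f = 0.

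**Adding the planned 10% dropout**, taken as random loss of period 2, at 5% v 0%: ITT stays at 2 to 3% for every f. PP goes from 8–9% at f = 0 to 48% at f = 1. Missing = success is about 7%.

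**The case against.** The strongest reply is that ITT is protected. The observed G-Pen failure still counts toward the 5% absolute condition and still widens the unpaired interval. Ordinary dropouts scored as failures make ITT conservative enough to mask the effect. All of this stands, and it means that a reader who infers that ITT, mITT and PP are biased to the same degree, or that the failure is erased in ITT, goes further than the documents allow. Only PP loses it outright.

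A reader might also infer that the protocol lets an unblinded investigator discard G-Pen failures. It does not say that. It permits non-completion without directing it, requires consultation with the Medical Monitor, states no preference by drug, and cancels GlucaGen failures in the same way. Only first-period failures are exposed.

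A paired limit would give larger ITT figures (about 35% at 5% v 0%, f = 1), but the only code shown is unpaired, so those figures should not be the headline.

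Finally, the SAP already plans the missing = success run, and SAP 5.3.1 already tabulates discontinuations with reasons by sequence. Both help. However, the run has no role in the decision, and the table does not cross the first drug with the first-period outcome. Masking by unrelated dropout also depends on how much dropout occurs; it does not correct the scoring.

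**Conclusion.** The concern holds in a limited form. As written, the scoring pulls the difference toward zero whenever a second visit is not done after a first-period failure. That is anti-conservative when G-Pen is the worse drug, which is the case the test exists to detect. One cancelled visit can reverse the result in ITT, mITT and PP when there are 3 failures against 0.

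The size depends on f, which is unknown. In PP the inflation is material in every setting examined. In ITT it is moderate at 5% v 0%, small at 6% v 1%, absent at 7% v 2%, and largely masked under 10% random dropout. If no visit is cancelled after a failure, there is no effect. The documents do not say that PP alone may support the claim, but they do not rule it out. Should-fix.

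**What to change.** Leave the clinical decision in Protocol 7.3 unchanged and amend the SAP before database lock.

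1. **SAP 6.5.** When period 2 is not given after an observed period-1 failure, count the observed failure and do not impute a failure for the drug not given. Say whether that missing cell is scored as a success or left out of the denominator. In the example above both give 5.21%, because 0/121 and 0/122 each add no variance.
2. **SAP 5.1.3 and 6.5.** State that PP alone cannot support the claim. Keep the both-doses definition, and add a supplementary PP run that retains these observed failures. Require the planned missing = success analysis to meet the same rule before non-inferiority is declared.
3. **Tables.** Report second visits not done, by first drug and first-period outcome.

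The cost is SAP wording and one or two outputs. The claim becomes harder to make if first-period G-Pen failures are not dosed again. For example, at a true 3% v 0% with f = 0.5 and no other dropout, ITT alone declares in 41% of trials, while missing = success declares in 29%, the same as when no visit is cancelled. So what is given up is the part produced by the scoring. With other dropout, missing = success is not exact (about 7% at 5% v 0%), so it should be required alongside ITT and not replace it.

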8. ELIGIBILITY CRITERIA AND STUDY ENROLLMENT

Subject eligibility should be reviewed and documented by an appropriately qualified member of the Investigator's study team before a subject is included in the study. Subjects must meet the following inclusion and exclusion criteria to be eligible for enrollment into the study.

8.1. Inclusion Criteria

1. Males and females diagnosed with T1D for at least 24 months. Women of childbearing potential require a negative urine pregnancy test and must use medically accepted contraception throughout the study and for 7 days after the last dose of study drug. Nursing mothers will be allowed to participate in the study. However, breast feeding during the inpatient study visits (Visits 2 and 3) and for 48 hours after each dose of study drug is not allowed.
2. Current usage of daily insulin treatment that includes having an assigned "correction factor" for managing hyperglycemia.
3. Age 18 to 75 years, inclusive.
4. Random serum C-peptide concentration < 0.6 ng/mL.
5. Willingness to follow all study procedures, including attending all clinic visits.
6. Subject has provided informed consent as evidenced by a signed and dated informed consent form (ICF) completed before any trial-related activities occur.

8.2. Exclusion Criteria

1. Pregnancy
2. Glycated hemoglobin (HbA1c) > 10% at Screening.
3. Body mass index (BMI) > 40 kg/m².
4. Renal insufficiency (serum creatinine greater than 3.0 mg/dL) or Stage 2 or greater kidney failure.
5. Serum alanine aminotransferase (ALT) or aspartate aminotransferase (AST) equal to or greater than 3 times the upper limit of normal.
6. Hepatic synthetic insufficiency as defined as a serum albumin of less than 3.0 g/dL.
7. Hematocrit ≤ 30%.
8. Blood pressure (BP) readings at Screening where systolic blood pressure (SBP) < 90 or > 150 mm Hg, and diastolic blood pressure (DBP) < 50 or > 100 mm Hg.
9. Clinically significant electrocardiogram (ECG) abnormalities.
10. Use of total insulin dose per day > 2 U/kg.
11. Inadequate venous access.
12. Congestive heart failure, New York Heart Association (NYHA) class II, III or IV.

13. History of myocardial infarction, unstable angina, or revascularization within the past 6 months.
14. History of a cerebrovascular accident or with major neurological deficits.
15. Active malignancy within 5 years from Screening, except basal cell or squamous cell skin cancers. Any history of breast cancer or malignant melanoma will be exclusionary.
16. Major surgical operation within 30 days prior to Screening.
17. History of or current seizure disorder (other than with suspect or documented hypoglycemia).
18. Current bleeding disorder, treatment with warfarin, or platelet count below 50×10^9 per liter.
19. History of pheochromocytoma or disorder with increased risk of pheochromocytoma (multiple endocrine neoplasia type 2 [MEN 2], neurofibromatosis, or Von Hippel-Lindau disease).
20. History of insulinoma.
21. History of allergies to glucagon or glucagon-like products, or any history of significant hypersensitivity to glucagon or any related products or to any of the excipients (DMSO and trehalose) in the investigational formulation.
22. History of glycogen storage disease.
23. Subject tests positive for human immunodeficiency virus [HIV], hepatitis C virus [HCV], or hepatitis B virus [HBV] infection (hepatitis B surface antigen positive [HBsAg⁺]) at Screening.
24. Active substance or alcohol abuse (more than 21 drinks per week for male subjects or 14 drinks per week for female subject).
25. Administration of glucagon within 7 days of Screening.
26. Participation in other studies involving administration of an investigational drug or device within 30 days or 5 half-lives, whichever is longer, before Screening for the current study and during participation in the current study.
27. Any other reason the Investigator deems exclusionary.

8.3. Randomization

Subjects who meet all eligibility criteria, who reach the baseline euglycemia steady state, and who the Investigator deems appropriate to begin the induction procedure (see Section 10.2) at the first treatment visit will be randomized for the study. The randomization schedule will be produced by the Study statistician a priori for loading and implementing in the Interactive Web-based Randomization System (IWRS). Using a permuted random block assignment, stratified by site, subjects will be randomly assigned to receive either Treatment Sequence 1 (G-Pen → GlucaGen Hypokit) or Treatment Sequence 2 (GlucaGen Hypokit → G-Pen).

Once a subject has been randomized, information regarding the glucagon (G-Pen or GlucaGen Hypokit) to be administered to the subject at each of the treatment visits will be viewable by study staff in the Dose Administration form in the electronic data capture (EDC) system.

